2.5 Statistical analysis, confidentiality plan

In terms of statistical analysis, SPSS 27.0 statistical software is used to establish a database and perform statistical processing. Descriptive statistical analysis, qualitative indicators are described as percentages, and quantitative indicators are described as mean \pm standard deviation. The data is subjected to normality testing and corresponding testing methods are adopted based on whether it follows a normal distribution. Qualitative data comparison adopts chi square test. Quantitative data conforms to normal distribution, t-test is used for comparison between two groups, and nonparametric test is used for abnormal distribution and $P < 0.05$ is considered statistically significant.

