2.2 Study Description

The aim of this study is to observe the therapeutic effect of Baduanjin on improving physical fitness and bone density in MHD patients. A total of 50 MHD patients will be included and randomized into an intervention group of 25 cases and a control group of 25 cases. The intervention group undergo a 30 minute Baduanjin exercise under the guidance of a professional doctor before the dialysis day, including a 5-minute warm-up exercise, a 20 minute Baduanjin exercise, and a 5-minute relaxation exercise. The intervention group practice three days a week, while the control group maintain routine treatment and daily activities. Measure the indicators of each group at baseline, months 6, 12. The evaluation of physical fitness is based on the scores (which include muscle strength measurement; five-times sit-to-stand test; timed "up and go" test; sitting forward flexion test; standing on one-leg with eyes closed test). The bone mineral density test is based on the result of the double-energy DXA line. The quality of life score is based on the SF-36 score, and the emotional

score is based on the anxiety and depression scale.

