The sitting forward flexion test is often used to evaluate the flexibility of the lower limbs of patients. The patient straightened the knee joint, sat on the flat ground with both feet flat on the test board, bent forward, straightened both arms forward, and gradually pushed the cursor with both middle fingertips to the farthest possible distance. The measuring device was 0 point along the plane of the foot pedal board, negative inward, positive forward, in centimeters. The knee joint could not be bent during the test, and sudden force could not be applied. The test was conducted 3 times in total, and the best result was taken for statistical analysis.

5) The Standing on one-leg with eyes closed test (SOLECT)

The Standing on one-leg with eyes closed test evaluates the stability of the static posture by quantitative measurement, reflecting the balance ability of patients. The patient spread both hands, closed his eyes, and stood on one leg, with the other leg bent so that the angles between the two legs were 90 degrees. Time was recorded from the time when the foot left the ground, and the shaking stopped when the foot left the ground or stood up. The average of the three times was used for statistical analysis.

6) Bone mineral density test

The signals received by the scanning system after the double-energy DXA line penetrated the body were transmitted to the supporting software to calculate the average bone mineral density content (g/cm²) of the whole body, the left femur Ward triangle area, and the lumbar spine (L2~L4).

Secondary Outcome Measures:

1) Changes in the Short Form-36 (SF-36)

Changes from the Short Form-36 (SF-36) and European Quality of Life Five Dimension (EQ-5D-5L) scale at 0 months, 6 months, 12 months. The SF-36 score is used to evaluate an individual's health status and quality of life. The SF-36 score expressed as a number between 0 and 100, with higher numbers indicating better health. EQ-5D-5L evaluate quality of life from five aspects: action ability, self-care, daily activities, pain or discomfort, anxiety or depression. The score range generally ranges from less than 0 to 1, and the higher the score, the better the state; The VAS score range is 0-100, with higher scores indicating better health status.

2) Changes in the Hospital Anxiety and Depression Scale (HADS)

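### Section 2.5 plans only group means, SDs and a P value from a test chosen by the data: no between-group estimate or confidence interval, and no fixed method per outcome

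*Combined protocol and SAP*

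**What the plan says.** Section 2.5 holds the whole statistical plan in the available text. It says "The data is subjected to normality testing and corresponding testing methods are adopted based on whether it follows a normal distribution". For quantitative data, "t-test is used for comparison between two groups, and nonparametric test is used for abnormal distribution". A P value below 0.05 "is considered statistically significant". All such data are summarised in one way: "quantitative indicators are described as mean" and standard deviation.

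The rule covers every quantitative outcome in Section 2.4: six measures listed as primary, plus SF-36, EQ-5D-5L and HADS. Section 2.4 fixes how each patient's value is formed (for the one-leg stand, "The average of the three times was used for statistical analysis"), but ties no between-group method to any outcome. Section 2.2 sets the size and visits: "A total of 50 MHD patients will be included and randomized into an intervention group of 25 cases and a control group of 25 cases" and "Measure the indicators of each group at baseline, months 6, 12".

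The plan does not name the normality test, its level or the nonparametric test. Nor does it say whether normality is judged by arm or pooled, on values or changes, or once per outcome or at each visit.

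**The concern.** Three things follow from the text.

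- **No estimate of effect.** The planned output is a group summary and a P value. With 25 per arm, a non-significant P value cannot separate absence of effect from lack of information. Section 1 wants data to support exercise rehabilitation, and that needs an effect size with its uncertainty.
- **Summary and test can disagree in kind.** An outcome the rule calls non-normal goes to a rank test but is still described by mean and SD. The reader would see a difference in means beside a P value that does not test means.
- **The comparison is not fixed in advance.** Whether an outcome is judged on means or on ranks is settled only after its data are seen. Nothing prevents the answer from differing between months 6 and 12, in which case the two results for one outcome are not on the same footing.

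**Working it through.** The plan gives no SD, effect size or power, so there is no stated figure to reproduce. Two checks apply.

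**1. Behaviour of the rule (simulation).**

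Inputs from the documents: 25 per arm (Section 2.2), months 6 and 12 (Section 2.2), P < 0.05 (Section 2.5; two-sided assumed).

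Assumptions, because the plan is silent: Shapiro-Wilk at 5% in each arm at each visit; t-test if both arms pass, otherwise Mann-Whitney; correlation 0.8 between visits; normal or log-normal data. There were 2,000 to 8,000 trials per scenario, and the ranges below span repeat runs. Disagreement is shown for a real effect giving about 70% power.

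| Data | Rank test chosen | Different tests at months 6 and 12 | t-test and Mann-Whitney disagree on P < 0.05 |
|---|---|---|---|
| Normal | 9–11% | 15–18% | 6% |
| Log-normal, CV 0.25–0.3 | 39–50% | 35–38% | 8–9% (CV 0.3, ratio 0.8) |
| Log-normal, CV 0.5 | 83–84% | 22% | 10% (ratio 0.7) |
| Log-normal, CV 0.8–1.0 | 98–99% | 1–4% | 16–18% (ratios 0.6, 0.55) |

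Hand check, normal data: the chance that at least one arm fails is 1 − 0.95² = 0.0975. If the visits were independent, they would receive different tests with probability 2 × 0.0975 × 0.9025 = 0.176. Positive correlation lowers this: simulated 17.5% at correlation 0.5 and 15.4% at 0.8. The same formula gives 2 × 0.5 × 0.5 = 0.50 when the rank test is chosen half the time (CV 0.3), and 2 × 0.98 × 0.02 = 0.039 at CV 0.8. Both are consistent with the table. A correlation of 0.5 raises the figure at a log-SD of 0.25 (CV = √(exp(0.25²) − 1) = 0.25) from 36% to 46%.

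The last two columns must be read within a row. The pre-test can change the verdict at a visit only in trials where the two tests disagree. At CV 0.3, where switching is common, that is at most about 9% of trials. At CV 0.8–1.0 disagreement is larger, but the rule picks the rank test almost every time.

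Without a true effect, the tests disagree in about 2% to 3% of trials, and the rule rejects in 4.0% to 5.7%. The Monte Carlo standard error with 2,000 trials is √(0.05 × 0.95 / 2000) = 0.5 points.

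Power, rule against a prespecified log-scale t-test:

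- CV 0.3: 0.744 against 0.753
- CV 0.5: 0.712 against 0.738
- CV 0.8: 0.698 against 0.728
- CV 1.0: 0.670 against 0.698

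The gaps are 0.9, 2.6, 3.0 and 2.8 points (0.5 to 3.6 across repeat runs).

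**2. Precision that would go unreported.**

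The half-width of a 95% CI for an unadjusted mean difference, in SD units with all 50 patients analysed, is t(0.975, 48) × √(2/25) = 2.011 × 0.283 = 0.569.

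As an illustration, an observed difference of 0.30 SD would be non-significant, with an interval of 0.30 − 0.57 = −0.27 to 0.30 + 0.57 = 0.87 SD. That includes no effect. It also includes 0.79 SD, the difference that 25 per arm detects with 80% power: (1.960 + 0.842) × 0.283 = 0.79. A P value alone shows none of this.

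**The case against.** The strongest reply is that the rule does little measurable harm. Type I error is near nominal and the power loss is small. Even that loss is measured on log-normal data, which favour a log-scale analysis. Disagreement between tests is not peculiar to the rule: a prespecified log-scale t-test also disagrees with Mann-Whitney in 6% to 7% of the same trials, and with the raw-scale t-test in 6% to 18%. All of this stands.

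Some stronger readings are tempting and should not be drawn:

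- **That the choice of test is close to random.** This fits only CV 0.25–0.3. For normal data the rule mostly keeps the t-test, and from CV 0.5 upward it mostly picks the rank test.
- **That 38% switching goes with 18% disagreement.** These come from different degrees of skew.
- **That the plan prescribes a switch between visits.** The text only permits it. Testing by arm and visit is an assumption, and SF-36, EQ-5D-5L and HADS are defined as changes, which may be less skewed than raw times.
- **That mean minus SD would fall below zero for the timed tests.** This needs a CV above 1, and the documents give no mean or SD for any of them.
- **That a rank test can yield only a P value.** A Hodges-Lehmann shift with an interval can accompany it. The gap is that the plan asks for no estimate at all.

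It can also be said that readers could derive a mean difference from the group summaries. They could, but the plan does not commit to that difference or its interval, and it would not match a rank test.

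**Conclusion.** The point holds as one of estimand and reporting. From the text alone: no between-group estimate or confidence interval is planned, mean and SD would accompany rank tests, and no outcome has a method fixed before its data are seen.

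The size of the month 6 to month 12 inconsistency depends on the assumed way of applying the rule and on skewness, neither of which the documents give. It is largest at mild skew and almost vanishes at strong skew, where the remaining fault is a rank P value beside a mean and SD.

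A reader might infer inflated false positives. The simulation does not support that.

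This is a cheap improvement, not a flaw that invalidates the trial.

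**What to change.** In Section 2.5, replace the normality-test rule with one prespecified analysis per outcome, used at both months 6 and 12, that reports the between-group difference with its 95% CI. A linear model is one way, and it can also carry the baseline value that Section 2.2 already collects. State the scale of each outcome before any outcome data are seen. The documents contain no distributional data that would dictate a particular transformation, so that choice belongs to the sponsor; what matters is that it is made in advance. Keep the rank test as a labelled sensitivity analysis, and give median and quartiles beside the mean for skewed variables.

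The cost is a few sentences, with no extra patients or visits, and SPSS 27.0 can do it. The downside is that the scale must be chosen without sight of the data, and any outcome reported as a ratio needs a line of explanation.

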2.4 Outcome Measures

Primary Outcome Measure:

1) Muscle strength measurement

Grip strength can reflect the strength of hand muscles. The grip strength of both hands of patients was measured using a domestic gripper. The patient took an upright position and grasped the handle with the maximum force. When the display on the machine stopped changing, the value was recorded. The test was repeated three times, and the maximum value was taken to record the results.

2) Five-times Sit-to-Stand Test (FTSST)

The five-times sit-to-stand test is used to evaluate the functional strength of the lower

limbs. MHD patients sat on a 46cm chair without armrests, with their feet on the ground and their backs not resting on the chair. Their hands were crossed on their shoulders. They stood up from the chair as quickly as possible without arm support. They completed five sitting and standing movements, and the completion time was recorded. During the test, the patient kept his hands crossed and his knees completely straightened. Three tests were completed, with a one-minute rest between tests. The average value of the three tests was statistically analyzed.

3) Timed "up and go" test (TUGT)

The timed "up and go" test is often used to evaluate functional mobility such as balance and walking required in daily life. MHD patients were seated in a back chair with armrests (the seat was about 46cm high, and the armrest was about 21cm high). A guide line was placed on the ground 3m away from the chair. After the test began, the patient left the chair, stood firmly and walked forward for 3m as fast as possible, crossed the guide line, turned around, and returned to the chair to sit down. The walking aids were not allowed during the test. The test was conducted 3 times in total, with a 1-minute rest between adjacent tests. The average value of the 3 tests was taken for statistical analysis.

4) The sitting forward flexion test

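### Six primary outcomes (8 or 9 variables) at two visits are judged by P < 0.05 alone, with no lead variable, primary visit or multiplicity control

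*Combined protocol and SAP*

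**What the plan says.** Section 2.4 places six measures under one primary-outcome heading, unranked: grip strength, five-times sit-to-stand, timed up-and-go, sitting forward flexion, one-leg standing with eyes closed, and bone mineral density (BMD).

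- **BMD** is three variables, because it is calculated "of the whole body, the left femur Ward triangle area, and the lumbar spine (L2~L4").
- **Grip** is one or two. The text says "The grip strength of both hands of patients was measured using a domestic gripper" and then "The test was repeated three times, and the maximum value was taken to record the results", without saying whether that maximum is per hand or overall.
- **Visits.** Section 2.2 says "Measure the indicators of each group at baseline, months 6, 12" and gives neither post-baseline visit priority.
- **Composite.** Section 2.2 also says "The evaluation of physical fitness is based on the scores", but no rule for scoring or combining the five fitness tests appears.
- **Analysis.** Section 2.5 says "t-test is used for comparison between two groups, and nonparametric test is used for abnormal distribution", and sets the threshold: "P < 0.05$ is considered statistically significant". It does not state sidedness.

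The documents contain no hierarchy, no division of alpha, no multiplicity adjustment and no rule that all primaries must succeed.

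**The concern.** Section 2.2 states the aim as to "observe the therapeutic effect of Baduanjin on improving physical fitness and bone density in MHD patients". Eight or nine variables at two visits give 16 to 18 primary comparisons, each with its own 5% chance of a false positive. The plan does not say which comparison, or how many, must be significant before that effect is claimed. The claim could therefore rest on whichever variable and visit happens to fall below 0.05, and 5% would not be the error rate of the trial's main conclusion. Choosing the variable or visit after seeing the group results cannot repair this.

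**Working it through.** **Inputs from the documents.** 25 patients per group (section 2.2); k = 8 or 9 primary variables (section 2.4); visits at months 6 and 12 (section 2.2); threshold 0.05 per test (section 2.5).

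**Assumptions.** Tests are two-sided, each visit is tested separately, and any one significant result counts. The documents give no correlations, so ranges are used.

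**The plan's own figure.** There is none to reproduce. The documents state no family-wise error rate, and give no effect size, SD or power behind the total of 50.

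**Step 1: independent tests (in effect a ceiling).** Chance of at least one P < 0.05 under no effect = 1 − 0.95^k.

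- One visit: 1 − 0.95^8 = 33.7%; 1 − 0.95^9 = 37.0%.
- Both visits: 1 − 0.95^16 = 56.0%; 1 − 0.95^18 = 60.3%.

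**Step 2: correlated tests.** Null trials were simulated with 25 per arm, multivariate normal data and two-sample t-tests (40,000 trials per setting, simulation error about ±0.5 points). The correlation between two variables at different visits was taken as the between-variable correlation times the between-visit correlation. The last two rows use a normal approximation to the test statistics.

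| Between-variable correlation (between-visit 0.7–0.9) | One visit | Both visits |
|---|---|---|
| 0.2–0.5 | 25–35% | 34–52% |
| 0.7 | 19–21% | 26–32% |
| 0.8 | 16–17% | 21–26% |
| Structured: fitness 0.2–0.5, BMD sites 0.5–0.7, fitness with BMD 0.1–0.3, two hands 0.8–0.9 | 26–33% | 35–50% |

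The ends of the first row are k = 8 at correlation 0.5 (25.3%; 34.0% with between-visit 0.9) and k = 9 at 0.2 (35.1%; 51.9% with between-visit 0.7).

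**Step 3: false results favouring Baduanjin only (nominal 2.5%).** If independent, 1 − 0.975^k gives 18.3% and 20.4% for k = 8 and 9, and 33.3% and 36.6% for 16 and 18. By simulation the rates are 13–18% at one visit and 17–28% over both at correlation 0.2–0.5, and 9–10% and 13–16% at 0.7.

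**Step 4: Holm at month 12.** The first step uses 0.05/8 = 0.00625 or 0.05/9 = 0.00556. The simulated chance of any false primary result is 3–5% at every correlation from 0.2 to 0.7.

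**Step 5: what that costs.** Difference detectable with 80% power, from the noncentral t:

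| Alpha | 25 per arm | 20 per arm (assumed remaining) |
|---|---|---|
| 0.05, unadjusted | 0.81 SD | 0.91 SD |
| 0.00625 (8 variables) | 1.05 SD | 1.19 SD |
| 0.00556 (9 variables) | 1.07 SD | 1.20 SD |

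With only two primaries the first Holm step is 0.025, and the detectable difference at 25 per arm is 0.90 SD.

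**Step 6: a five-test composite as one of two primaries.** If m of the five tests shift by 0.5 SD and the tests correlate at rho, the effect on their standardised mean is 0.5·m/√(5(1 + 4·rho)).

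- m = 5: 2.5/√11 = 0.75 SD at rho 0.3 and 2.5/√15 = 0.65 SD at rho 0.5, giving 64% and 49% power at alpha 0.025.
- m = 2: 1/√11 = 0.30 SD and 1/√15 = 0.26 SD, giving 11% and 9% power.

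**The case against.** The strongest objection is that the headline figures depend on a decision rule the plan never states. It does not say that both visits are tested separately or that one significant result is enough. Other readings give other rates. With 8 variables, fitness correlation 0.3–0.5, BMD 0.6–0.8, cross-domain 0.1–0.2 and between-visit 0.7–0.9:

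- If a claim needs a significant result in both fitness and bone density, the false-claim rate under no effect at all is about 2–3% at one visit and 3–7% over both.
- If the two domains are separate claims, the one-visit rates are about 18–21% for fitness and 10–12% for BMD.

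This stands as a limit on the figures. It does not rescue the plan, which states none of these rules. Even under the both-domains rule, if one domain truly responds, the other's error rate is still 10–21%.

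The correlations and two-sided testing are indeed assumed, and the both-visits figure leans on them most; the one-visit figure is the safer of the two.

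Nothing in the documents favours month 12 over month 6, or one testing family over one per domain. That is fair: what matters is that visit and family are fixed in advance, and month 12 with Holm is one sound way to do it.

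Finally, a 50-patient study could be labelled exploratory throughout. The plan does not do that. It calls these outcomes primary, sets a significance threshold and speaks of a therapeutic effect.

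**Conclusion.** The concern holds. Applied as written, section 2.5 does not control the error rate of the primary conclusion. The 25–35% (one visit) and 34–52% (both visits) figures assume two-sided tests, between-variable correlations of 0.2–0.5, between-visit correlations of 0.7–0.9, and a positive reading of any single significant primary. The conclusion does not depend on those correlations: at 0.8 between variables, the one-visit chance is still more than three times the nominal 5%. Counting only results that favour Baduanjin roughly halves the two-sided rates but leaves them several times the nominal 2.5%. This needs to be corrected before any outcome is compared between groups.

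**What to change.** Amend sections 2.4 and 2.5 before any outcome data are compared by group:

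1. Name month 12 as the primary visit, with month 6 supportive.
2. State whether grip is one value or one per hand, which fixes the count at 8 or 9. So that each p-value is uniquely defined, also state which leg the one-leg standing test uses and whether month-12 values or changes from baseline are compared.
3. Apply Holm's procedure at an overall two-sided 0.05 across those variables at month 12, using the p-value from whichever test section 2.5 selects.
4. Report every estimate with a 95% confidence interval, and call a primary result significant only if it passes Holm.

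The sponsor may instead pre-name fewer primaries, for example one fitness variable or score and one BMD site, tested by Holm. This costs less power. A composite helps only if most of the five tests respond.

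**Cost.** No new patients or measurements. Section 4.1 requires ethics approval before a revision is implemented. Power falls: for a true 0.8 SD effect on a given variable at 25 per arm, from 79% unadjusted to about 48–50% if two variables respond, or 59–61% if all do (simulated, 20,000 trials per setting, correlation 0.2–0.5).

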2.6 Preservation and Confidentiality of Information

The researcher preserves all research data, including confirmation of all participants (able to effectively verify different record materials, such as hospital original records), all original informed consent forms with subject signatures, all case

[键入文字]

observation forms, detailed records of evaluation indicators, etc.

The results of this project may be published in medical journals, but we will keep the information of the subjects confidential in accordance with legal requirements. Unless required by relevant laws, the personal information of the subjects will not be disclosed. When necessary, research supervision and management departments, hospital ethics committees and their relevant personnel may access patient information in accordance with regulations.

3. Exit and Termination Criteria

1. patients with adverse reactions such as trauma, surgery or serious infection, cardiopulmonary failure, who cannot continue to perform exercise during the trial;
2. Patients who underwent kidney transplantation or disappeared or died for various reasons during the trial;
3. Patients with poor compliance during the trial, unwilling to continue to exercise or requesting to withdraw from the trial for various reasons.

4 Ethical issues

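### The planned two-sample test at month 12 makes no use of what was measured in patients who left, and is biased if outcome-related exits differ between arms; a mixed model on all visits would use those data

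*Combined protocol and SAP*

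**What the plan says.** Section 2.2 gives the design: patients are "randomized into an intervention group of 25 cases and a control group of 25 cases", with the instruction "Measure the indicators of each group at baseline, months 6, 12".

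Section 2.5 gives the whole inferential plan for quantitative outcomes: if the data are normal, a "t-test is used for comparison between two groups, and nonparametric test is used for abnormal distribution". It names no analysis set, covariate, repeated-measures model or missing-data rule. It does not say whether the variable tested is the month-12 value or the change from baseline.

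Section 3 (Exit and Termination Criteria) lists three routes out:

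- Item 1: patients with adverse reactions "who cannot continue to perform exercise during the trial".
- Item 2: "Patients who underwent kidney transplantation or disappeared or died for various reasons during the trial".
- Item 3: "Patients with poor compliance during the trial, unwilling to continue to exercise or requesting to withdraw from the trial for various reasons".

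It gives no expected exit rate. It does not say whether leavers are still measured or how their data enter the analysis.

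**The concern.** A two-sample test at month 12 needs a month-12 value from each patient it includes. A patient who dies, disappears or withdraws after month 6 contributes nothing to it, although the trial holds a baseline and a month-6 value for that patient. Those values may still enter a month-6 comparison, but they cannot correct the month-12 one.

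Two features of section 3 make this more than a loss of precision. Item 2 applies in both arms, and continued follow-up cannot recover a month-12 value after death or disappearance. Items 1 and 3 are framed around exercise, which only the intervention arm is assigned. The reasons for leaving can therefore differ by arm. If they also relate to the outcome, the patients left at month 12 are no longer comparable, and with 25 per arm a few such exits can move the estimate.

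**Working it through.** The plan states no power, effect size, SD or exit rate, so there is no figure of its own to reproduce. The check is illustrative.

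**Inputs.** From the documents: 25 per arm and three visits. Assumed: SD 1 at each visit; correlations 0.75 (baseline to month 6), 0.85 (month 6 to month 12) and 0.70 (baseline to month 12); true effect 0.5 SD. Differences are Baduanjin minus control with higher scores better, so signs reverse for timed tests.

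**Exit patterns, chosen to be extreme.**

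- Pattern 1: the three controls with the lowest month-6 values leave, plus two random controls and three random Baduanjin patients.
- Pattern 2: the three lowest controls and the three highest Baduanjin patients leave.

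**Step 1: shift at month 6.** The expected values of the three lowest of 25 standard normal observations are -1.965, -1.524 and -1.263, which sum to -4.752. Removing them raises the mean of the other 22 by 4.752/22 = 0.216 SD. Random exits add no expected shift.

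**Step 2: shift carried to the other visits.** Month 12: 0.85 × 0.216 = 0.184. Baseline: 0.75 × 0.216 = 0.162.

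**Step 3: bias in pattern 1, by estimator.**

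- Raw month-12 means: -0.184.
- Baseline-adjusted, slope 0.70: -(0.184 - 0.70 × 0.162) = -0.07. Selection flattens the fitted slope a little, so simulation gives -0.07 to -0.08.
- Change from baseline: -(0.184 - 0.162) = -0.02.
- Using baseline and month 6: the regression weights are (0.70 - 0.75 × 0.85)/(1 - 0.75²) = 0.143 and (0.85 - 0.75 × 0.70)/(1 - 0.75²) = 0.743. The bias is -(0.184 - 0.143 × 0.162 - 0.743 × 0.216) = 0.00.

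In pattern 2 both arms shift, in opposite directions, so the raw bias doubles to -0.37 and the change-score bias to -0.04.

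**Step 4: simulation** (4,000 trials or more per pattern) agrees. Bias in SD:

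| Estimator | Pattern 1 | Pattern 2 |
|---|---|---|
| Raw month-12 means | -0.18 | -0.37 |
| Baseline-adjusted | -0.07 | -0.17 |
| Change score | -0.02 | -0.04 |
| Model also using month 6 | 0.00 | 0.00 |

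With no true effect, the raw t-test rejects in 11% (pattern 1) and 28% (pattern 2) of trials, against a nominal 5%.

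**Step 5: what drives the bias.** A second simulation had no true effect, equal correlations of 0.6 or 0.8, and exit probability depending on the month-6 value (logistic slope 1.5 per SD) or random. For the raw month-12 t-test:

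| Exits | Bias (SD) | Type I error |
|---|---|---|
| 30% outcome-related in one arm, 10% random in the other | 0.19 to 0.26 in size, either sign | 8.7% to 13.0% |
| 20% each, opposite mechanisms | +0.27 to +0.36 | 14.3% to 22.4% |
| 20% each, same mechanism | about 0 | 4.5% to 5.1% |
| 30% versus 10%, both random | about 0 | 4.2% to 5.0% |

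The likelihood estimate using baseline and month 6 was within 0.003 SD of zero throughout.

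**Step 6: precision with 20% random loss (20 per arm left).** Raw: √(2/20) = 0.316. Baseline-adjusted: √(2/20 × (1 - 0.70²)) = 0.226. Simulation gives about 0.32 and 0.23, and 0.22 when month 6 is added. Most of the gain comes from baseline adjustment. Month 6 adds about 4-5% (0.228 to 0.218, or 0.232 to 0.221).

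**The case against.** The strongest reply is that the plan never says it analyses completers only. Section 2.5 names types of test, and section 3 lists exits without saying that data are dropped. A reader might infer that the month-6 data are thrown away; the documents do not support that, because a month-6 comparison could use them. What stands is narrower: no two-sample test at month 12 can use a patient without a month-12 value.

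The second reply is that the size depends on the variable tested. Section 2.4 describes the secondary outcomes as changes, and on change scores the bias is only -0.02 to -0.04 SD. This is a fair point. However, the small figure arises because the bias is 0.216 × (0.85 - 0.75) per affected arm, so it relies on two assumed correlations being close. For the primary outcomes the variable is not specified, and raw month-12 values remain a possible reading.

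The third is that the patterns are severe, and this stands too. If three controls leave against one Baduanjin patient, with exit merely more likely at low month-6 values (log-odds 1 per SD), the raw bias is -0.07 SD against a standard error of 0.29. If two low and one high control leave against one low and one high Baduanjin patient, it is -0.06 SD.

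Finally, the zero for the mixed model is partly built in, since exit was made to depend on month-6 values. When exit follows the unseen month-12 state instead, the model's bias is -0.06 and -0.14 SD in analogues of the two patterns, against -0.21 and -0.43 SD for raw means. The model is better, but not unbiased.

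**Conclusion.** The point holds as a weakness in the analysis choice, and the plan should be changed. The named test cannot use the earlier data of patients who leave. If exits relate to outcome and differ between arms in mechanism or extent, the raw month-12 comparison is biased, in either direction.

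Two stronger readings should be avoided. One is that an imbalance of two or three exits is itself enough: uneven random exits give no bias, while equal numbers leaving for opposite reasons give the largest. The other is that 0.2 to 0.4 SD is the bias to expect: those values come from extreme patterns and assumed correlations, because the documents supply neither exit rates nor correlations. That transplant removes fitter patients is plausible but not documented, and the argument does not need it.

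All three exit items matter. Items 1 and 3 may be the stronger source of imbalance, but how far they create missing values depends on whether those patients are still measured, which the plan does not say.

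**What to change.** In section 2.5, state that each continuous outcome is analysed in all randomised patients, as assigned, with one linear mixed model. Include baseline, month 6 and month 12, an arm-by-visit effect, a common baseline mean for the two arms and an unstructured covariance. Read the month-6 and month-12 differences from that model.

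Tabulate exits by reason and arm for all three items of section 3. Add a sensitivity analysis for exit that observed data do not explain, for example one that ranks patients who died worst.

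The cost is wording and a little more analysis work in SPSS, which the plan already uses; no visits or patients are added. The downside is the assumption that exit is explained by measured values, which is why the sensitivity analysis is needed. For patients who leave before month 6, the model has only their baseline to work with.
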